### **Overview of the Proposed Intervention Conditions**

We propose to randomize youth into one of two conditions, outlined below.

**Qlarity.** Subjects randomized to Qlarity will be provided in-person assistance in loading the Qlarity app onto their phone immediately following their baseline interview and assessment. Once the app is loaded onto their phone, participants will generate a username and password. The proposed modules will each include a teaching and a practice component that uses mindfulness techniques to reduce or avoid substance use. Modules will be “unlocked” in ascending order as participants move through the program (i.e., module 2 will be “unlocked” after completion of module 1, etc.).

**Drug Court, Group Therapy and Case Management (DC).** The DC youth will receive the usual services provided by the DHS for youth who present with drug and alcohol use, which includes involvement in drug court, and case management services for the youth and their parents that span the duration of the youth’s probation or formal accountability contract. The drug court and case management services are provided by probation officers through the DHS. The DHS will manage each case and will make all decisions on referrals to community resources, including individual therapy, family therapy, mandated urine screens, and/or inpatient or outpatient substance use treatment that might occur in addition to the typical youth skill building groups and case management services. None of the usual services that youth in the respective study conditions receive will be affected by their participation in the study. We will track the youths’ and parents’ use of services as part of the interviews with a service utilization measure and official DHS reports of urine screens at each assessment. With these data, we will examine the type and length of treatment received for youth in both conditions, as well as the timing and outcome of urine screens over the course of the study. This services utilization measure has been used in previous work and has been useful for examining treatment impact.

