**Measures:** The following measures will be used to examine baseline demographic and pre- and post-changes in mindfulness skills, emotion regulation, and substance use: 1) Demographics, 2) Alcohol and Drug Use Survey, 3) Cigarette Use, 4) Adolescent Attitudes Questionnaire, 5) Emotion Regulation Scale, 6) Five Facet Mindfulness Questionnaire, 7) Youth Substance Use Interview (including Services Utilization), and 8) Qlarity usability and satisfaction rating. The Alcohol and Drug Use Survey is a 48-item scale that combines the Michigan Alcohol Screening Test (MAST) and the Drug Abuse Screening Test (DAST) and the Self-Efficacy for Limiting Substance Use. These scales are widely used as measures to assess the level and frequency of alcohol and drug use, use of mindfulness skills, as well as the ability to limit substance use, and have been shown to have good psychometric properties. In addition, urinary drug tests will be conducted at the baseline, 1- and 3-month follow ups. UA results will be photocopied after completion, and the UA cups will be discarded immediately; no identifying information will be recorded on the UA cups. We will use the same UA drug testing procedure that we have found to be successful in our current NIH funded study with adolescents in the juvenile justice system. All data will immediately be moved to a secure, locked location within ORI/Influents Innovations accessible only to the PI and research staff. The Services Utilization Survey is an interviewer-administered instrument that collects information about a respondent's use of a wide range of services such as in- and out-patient medical care (hospital, clinic, or office based), mental health treatment, drug and alcohol abuse treatment, and

Table 1. Measures		Assessments		
Measure	Baseline	1 Month	3 Month	
Adolescent Attitudes Questionnaire	●	●	●	
Alcohol and Drug Use Survey (MAST/DAST)	●	●	●	
Qlarity Usability and Satisfaction		●	●	
Cigarette Use	●	●	●	
Demographics	●			
Emotion Regulation Scale	●	●	●	
Five Facet Mindfulness	●	●	●	
Urine Drug Screens	●	●	●	
Youth Substance Use Interview (Services Utilization)	●	●	●	

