health-related groups (e.g., Narcotics or Alcoholics Anonymous, or physical health groups). For each type of service accessed, there are questions regarding frequency, reason for the service (e.g., physical, mental health, substance-use related), insurance coverage and out-of-pocket expenses. The Five Facet Mindfulness Questionnaire is a 36-item self-reported questionnaire that queries aspects of mindfulness such as non-judgment. The Adolescent Attitudes Questionnaire is a measure of attitudes and beliefs regarding drug and alcohol that was adapted from an interview developed to test 12 mediators of drug use in adolescents. For this study, we will use the normative beliefs, lifestyle incongruence, beliefs about consequences, and commitment scales. The Emotion Regulation Scale is a 36-item self-report questionnaire designed to assess multiple aspects of emotion dysregulation. Program navigation and usability will be assessed for all participants and will include reports of: 1) ease of use, 2) perceived benefits of using the app, 3) likeability, and

4) suggestions for product development and modifications. Participants will provide ratings on product satisfaction and usability on a 7-point Likert Scale. Qualitative data gathered from the focus groups will be recorded and evaluated with the goal of identifying challenges to using the app, product satisfaction, and suggested product modifications. In addition to qualitative data gathered during the pilot evaluation study, login tracking information from the app will be used to assess each participant's: 1) frequency and duration of app use and 2) number of modules completed. These data will be used to evaluate treatment engagement and adherence.

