**Statistical design and power overview:** This project will test the efficacy of the Qlarity app in Year 2 with a randomized trial that nests multiple assessments nested with 380 youth within each of two conditions. Half of the participants will receive the Qlarity app intervention and half will maintain business-as-usual. We hypothesize that Qlarity app will increase youth's emotional regulation, mindfulness and self-efficacy and decrease alcohol, tobacco, and other drug use. Within this study design, we will test for main effects, moderation, mediation, and acceptability of the Qlarity app intervention and expect to detect effect sizes of 0.25 standard deviations. Program feasibility will be demonstrated via significant pre-post differences, a high and consistent level of app use, and a high degree of youth satisfaction ratings. See Human Subjects Statistical Design and Power section for complete details.

**Feasibility benchmarks:** Program feasibility will be demonstrated by the achievement of the following benchmarks: (a) significant pre-post increases (e.g., Cohen's  $d > .35$ ) in emotional regulation, mindfulness, and self-efficacy, (b) significantly greater decreases in alcohol, tobacco, and other drug use for Qlarity participants; (c) a high consistent level of app usage (e.g., over 70% of users used the app at least 12 times over the 12 weeks); and (d) a high degree of youth satisfaction and ratings of app acceptability and usability (mean ratings  $> 4.0$  on the 5-point scale). Benchmarks are based on meta-analysis quantitative methods that recommend effect sizes of at least  $d > .25$  to demonstrate educationally meaningful change; a desire to show at least an average of weekly app use by a majority of participants; and a level of participant satisfaction that meets or exceeds that of Phase I.

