**Feasibility benchmarks.** Program feasibility will be demonstrated by the achievement of the following benchmarks: (a) significant pre-post increases (e.g., Cohen's  $d > .35$ ) in emotional regulation, mindfulness, and self-efficacy, (b) significantly greater decreases in alcohol, tobacco, and other drug use for Qlarity participants; (c) a high consistent level of app usage (e.g., over 70% of users used the app at least 12 times over the 12 weeks); and (d) a high degree of youth satisfaction and ratings of app acceptability and usability (mean ratings  $> 4.0$  on the 5-point scale). Benchmarks are based on meta-analysis quantitative methods that recommend effect sizes of at least  $d >.25$  to demonstrate educationally meaningful change; a desire to show at least an average of weekly app use by a majority of participants; and a level of participant satisfaction that meets or exceeds that of Phase I.

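### Feasibility benchmark (d) sets its cut on a 5-point scale, but the plan collects the satisfaction and usability ratings on a 7-point scale

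*Combined protocol and SAP*

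**What the plan says.** The combined protocol and SAP states the feasibility benchmarks twice in the same terms: after the Statistical design and power overview (under Data Collection Procedures) and at the end of Data Analysis. Feasibility is to be shown by meeting four benchmarks, (a) to (d). The first statement of (d) sets the cut as "mean ratings $> 4.0$ on the 5-point scale", and the second asks for "ratings of app acceptability and usability (mean ratings $> 4.0$ on the 5-point scale". The figures in (a) and (c) are marked as examples; the figure in (d) is not. Part of the rationale given for the benchmarks is "a level of participant satisfaction that meets or exceeds that of Phase I".

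The instrument is described in the Measures text under Data Collection Procedures: "Participants will provide ratings on product satisfaction and usability on a 7-point Likert Scale". Apart from the benchmarks themselves, this is the only place that gives a response scale for these ratings. The list of measures has a single entry for them, "Qlarity usability and satisfaction" rating, and Table 1 schedules it at 1 month and at 3 months.

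On who provides ratings, the Measures text says "Program navigation and usability will be assessed for all participants". The Overview of the Proposed Intervention Conditions describes app installation for one arm only: "Subjects randomized to Qlarity will be provided in-person assistance in loading the Qlarity app onto their phone".

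**The concern.** A threshold can be applied only on the scale for which it was set. Here the threshold names one scale and the data collection names another, with nothing to link them. The number 4.0 can be reached on either scale, so the mismatch would not show itself at analysis. An analyst could compare a 7-point mean with 4.0 and report a pass without noticing that the required level of satisfaction had fallen.

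What is at stake is one of the four criteria for declaring the programme feasible. The intended comparison with Phase I is affected too, because it needs a common scale and the plan gives neither the Phase I scale nor its value. In addition, (d) names no arm and does not say whether the 1-month or the 3-month rating counts.

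**Working it through.** The cut is a chosen threshold, so the plan has no calculation to reproduce. The check is to place 4.0 on each scale.

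**Inputs from the document.** Cut above 4.0 on 5 points (Feasibility benchmarks, both statements); ratings on 7 points (Measures); 190 youth in the Qlarity arm (Efficacy Trial); about 10% not completing (Overview and timeline).

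**Assumptions.** Item coding is not given. For the 5-point scale I take 1-5: with 0-4 coding, 4.0 would be the maximum (4/4 = 100%) and no mean could exceed it. For the 7-point scale I take 1-7, with 0-6 as the alternative. Linear rescaling is a convention, not an established equivalence between instruments.

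**Position of 4.0 in the range**
- On 1-5: (4 − 1)/(5 − 1) = 0.75.
- On 1-7: (4 − 1)/(7 − 1) = 0.50, the midpoint.

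**Conversion**
- From 1-5 to 1-7: 1 + (4 − 1) × 6/4 = 5.5. The simple ratio 4/5 × 7 gives 5.6.
- From 1-7 to 1-5: 1 + (4 − 1) × 4/6 = 3.0.
- With 0-6 coding: 4/6 = 0.67 of the range, and 75% of the range is 0.75 × 6 = 4.5.

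The zone in which the two readings disagree is therefore about 4.0 to 5.5 with 1-7 coding, and about 4.0 to 4.5 with 0-6 coding.

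**Would sampling error blur this?** Little. If loss is equal by arm, 190 × 0.90 = 171 Qlarity youth provide ratings. With an assumed rating SD of 2.0, the standard error is 2.0/√171 = 0.153.
- True mean 4.3: z = (4.3 − 4.0)/0.153 = 1.96, so the observed mean exceeds 4.0 with probability .975. It exceeds 5.5 with probability below .001.
- True mean 5.2: the observed mean exceeds 4.0 with probability above .999. It exceeds 5.5 with probability .025, since z = (5.5 − 5.2)/0.153 = 1.96.

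With a smaller SD or all 190 rating, the separation is sharper. These figures only illustrate the consequence; the mismatch itself needs no calculation.

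**The case against.** The strongest reply is that (d) is not a bare 4.0. It says which scale it refers to, and nothing in the plan allows 4.0 to be applied to a 7-point form. Opposite verdicts need three things together: the 7-point form is the one used, the words naming the 5-point scale are overlooked, and the mean falls in the zone between the two cuts. If the 7-point sentence in Measures is the slip, the benchmark is right as written and no verdict changes. This stands in part. It means the size of the consequence is conditional, but the contradiction remains and has to be settled one way or the other.

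A second reply is that the arm is largely implied, since only youth given the app can meaningfully rate it. That also stands. A reader might infer from the all-participants wording that comparison-arm ratings enter the mean, but the description of app installation points the other way. A clarifying phrase is enough. The time point is open, since Table 1 has two ratings and (d) chooses neither.

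A third limit is that the 7-point sentence names satisfaction and usability, while (d) also names acceptability. No separate acceptability rating is described, so the mismatch is established for satisfaction and usability at least.

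**Conclusion.** The point holds as an internal inconsistency in current text: the cut in (d) and the instrument that supplies its data are on different scales, with no bridge between them. Its size is conditional. If the 7-point form is used with 4.0 unchanged and items are coded 1-7, the cut drops from 75% to 50% of the range, and means between about 4.0 and 5.5 change verdict. With 0-6 coding the zone narrows to about 4.0 to 4.5.

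Three stronger conclusions are tempting but not supported:
- A reader might infer that the plan accepts a neutral rating as success. It does not say so; either scale statement could be the slip.
- A reader might infer that the trial's conclusions on substance use are at risk. The efficacy tests and sample size do not use these ratings.
- A reader might infer that the other benchmarks fail in the same way, for example because (a) asks for "a) significant pre-post increases (e.g., Cohen's $d > .35$ ) in emotional regulation, mindfulness, and self-efficacy" without a between-arm comparison. That is a deliberate pre-post marker, (b) is comparative and must also be met, and the main-effects section already plans condition-by-time tests. In (c), 12 weeks of use fits the 3-month follow-up, and no passage ends app access at 4 weeks.

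Severity is minor. Confidence is high on the mismatch; which scale was intended cannot be determined from the documents.

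**What to change.** - Use one scale for these ratings in the Measures text and in both statements of the benchmarks, and give its coding and anchors.
- If the 7-point scale is kept, restate the cut on it: about 5.5 on 1-7 coding if the same relative position is intended. If the 5-point scale is kept, correct the Measures text and leave 4.0.
- Give the Phase I value on the same scale, so that the intended comparison can be made.
- State that (d) is computed in the Qlarity arm, and whether the 1-month or the 3-month rating decides it.

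The documents do not give the trial's current status. The choice should be fixed before anyone sees the ratings or, if some have been seen, recorded with its date and reason. The cost is wording only: no added participants, measures or visits.
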